#### STUDY SUMMARY

Study Title	Utility of 3-dimensional gait analysis in reference to clinical assessments to detect significant change after a cerebrospinal tap test in patients investigated for idiopathic normal pressure hydrocephalus
Internal ref. no. (or short title)	Utility of 3D gait analysis in iNPH
Study Design	Cross-sectional, controlled study
Study Participants	People with iNPH and healthy control participants
Planned Size of Sample (if applicable)	20 people with iNPH 20 healthy volunteers of similar age and sex distribution
Follow up duration (if applicable)	N/A
Planned Study Period	12 months
Research Question/Aim(s)	We aim to provide a detailed characterization of gait impairment in people with idiopathic normal pressure hydrocephalus (iNPH) to aid diagnosis and provide a platform for future work to objectively assess the effectiveness of treatment interventions using gait analysis variables as the main outcome measure. Our primary objective is to identify key gait and balance variables that can objectively characterize the mobility impairment in iNPH and that will also serve as measures to accurately quantify changes in mobility and balance before and after lumbar puncture to remove cerebrospinal fluid (CSF tap test or TT), a standard clinical procedure to assess whether patients may benefit from permanent treatment with a neurosurgical operation to drain CSF (shunt). Whilst the emphasis will be placed on objective laboratory-based measures, this work will also seek

to validate robust clinical measures to support clinic-based assessments as potential surrogate measures and for instances where sophisticated gait analysis may not be accessible. We hypothesize that (i) those with iNPH will exhibit decreased gait velocity (slower walking), increased step width variability, unsteadiness (increased centre of mass trajectories), reduced joint ranges of motion, and poorer balance test scores, when compared to age-matched controls; (ii) gait outcome variables will improve following tap test; and (iii) gait analysis will be more sensitive than clinical
controls; (ii) gait outcome variables will improve following tap

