## 4.2 Outcome

The primary outcome measures of the 3D gait analysis are the 'dynamic balance' that evaluates the movement (sway) in the body centre of mass relative to the centre of pressure under the feet, step length, gait velocity and temporo-spatial measures of gait variability.

The discriminant performance between groups and the screening characteristics for shunt surgery of gait analysis variables will be compared with those of the current standard clinical assessments. These include: 10m timed walk (number of steps and seconds), 360 degree timed turns (number of steps and seconds), Tinetti gait and balance assessment (score out of 28), timed up and go test (seconds), 6m walk test (minutes and seconds), single leg stand (seconds), Romberg test(seconds).

Secondary outcome measures quantify general levels of everyday activity with a fitbit, levels of anxiety and depression with the hospital anxiety and depression scale (HADS, score out of 21), quality of life with the EQ 5D 5L and carer burden with the Burden Scale for Family Caregivers questionnaire (patients only), and the experience of gait analysis in controls and people with iNPH before and after TT in a semi quantitative interview.

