Psychological factors will be monitored in patients (part of the clinical routine) and controls (when they attend the gait laboratory) using the Hospital Anxiety and Depression Scale. Quality of life will be assessed with the EQ-5D-5L patient version (patients -part of the clinical routine- and controls when they attend the gait laboratory) and EQ-5D-5L proxy versions (patients only, part of the clinical routine) and carer burden will be assessed with the Burden Scale for Family Caregivers (patients only, part of the clinical routine). These secondary assessments will provide insight into clinically-relevant outcomes of everyday activity in the period immediately following tap-test and may be relevant for the participants' performance. We will also evaluate participants' experience and expectations of their gait and balance performance pre and post tap test when measured clinically and with gait analysis, assessing for concordance and participants' reaction to the results using a questionnaire. Patients are followed closely after the TT as part of clinical routine to discuss the results and plan further management.

Key gait and balance variables that can be used to characterize iNPH will be determined through the use of logistic (discriminant) regression analyses between patients and healthy controls. Given the sample size of this

initial study, variables will be considered unifactorially. A similar approach will be used to estimate the Receiver Operating Characteristic (ROC) curve for these variables as screening tools for shunt surgery. Standardised effect sizes for the key gait and balance variables will be compared informally with those derived for currently routine clinical measures by repeating the above analyses.

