# 6 STUDY SETTING

People with iNPH will be recruited from the regional specialist NPH clinic at The Manchester Centre for Clinical Neurosciences (MCCN) at Salford Royal Hospital, Northern Care Alliance, UK where they are assessed as part of their clinical routine by a senior neurologist with specialist interest in cognitive neurodegenerative disease, by a senior neuropsychologist with specialist interest in differential diagnostic assessments of patients with dementing disorders, advanced MRI scanning of the brain, lumbar puncture for cerebrospinal fluid neurodegeneration markers and clinical examination of gait and balance before and after TT carried out by a neurophysiotherapist prior to reaching a consensus diagnosis in the multidisciplinary team meeting (NPH MDT).

Healthy controls will be recruited in two ways. They may be spouses/carers of people with iNPH or they may be people from the general public who have responded to the study advertisement. We will aim to recruit the same number of controls as patients with a similar age and sex distribution but will not undertake individual matching.

Both groups will undergo the same laboratory-based testing protocols to assess their gait and balance in the gait laboratory at the MMU. Participants in the control group will be invited to attend a single testing visit at the gait laboratory. Participants with iNPH will be invited for a second test session the day after tap test to assess the effects of the procedure on gait (change score on outcome measures). Should the patient not feel well then this visit may have to be cancelled.

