#### 7.1.2 Exclusion criteria

Excluded are participants with

Other confirmed medical or surgical conditions better explaining symptoms than iNPH (patients) or with substantive impact (eg Parkinson's, osteoarthritis) as judged by the investigators (patients and control)

Secondary or obstructive hydrocephalus; previous surgical procedures for hydrocephalus (patients)

Amputation of lower limb/appendages

Musculoskeletal injury/recent lower-limb surgeries affecting gait or other musculoskeletal ailments affecting gait and balance performance as judged by the investigators.

Participants on specific medications (eg centrally acting) better explaining symptoms than iNPH (patients) or with substantive impact as judged by the investigators (patients and control)

Unable to carry out all study procedures.

Unable to comprehend informed consent.

- 7.2 Sampling
- 7.2.1 Size of sample

20 males and females with iNPH.

20 unmatched healthy volunteers of similar age and sex distribution.

We have determined the target sample size in anticipation that several gait variables will show complete discrimination between patients and controls and to develop preliminary estimates of variation (SD) in follow-up values and change scores following TT. We will also derive initial estimates of performance characteristics, such as area under ROC curve, for use of gait variables to screen for shunt surgery. Given the preliminary aims and multiplicity of candidate gait variables at this stage, all statistical significance values will be interpreted as indicative rather than definitive and no statistical power calculation would be appropriate

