#### 11.2 Appendix 2 – Schedule of Procedures (Example)

#### People with iNPH (research interventions only)

Procedures	Visits (insert visit numbers as appropriate)				
	Screening	Baseline	Tap test	Day after tap test	after day 7 post tap test
Informed consent	x				
Provision of fitbit	x				
Questionnaires pre TT (HADS, EQ-5D-5L patient and proxy versions, Burden Scale for Family Caregivers, expectations and experience of gait analysis, patient version)		x			
Gait analysis pre TT		х			
expectations and experience of gait analysis, patient version)				x	
Gait analysis post TT				х	
Collection of fitbit					x

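### The shunt-screening ROC analysis has no named reference standard and no listed shunt outcome, and each reference the text allows is either partly circular or beside the point

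*Protocol*

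**What the plan says.** Three places in the protocol commit to performance for shunt selection.

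- Section 4.2 sets two separate tasks: discrimination between groups, and a second one in which "the screening characteristics for shunt surgery of gait analysis variables will be compared with those of the current standard clinical assessments". The comparators are listed: "These include: 10m timed walk (number of steps and seconds), 360 degree timed turns (number of steps and seconds), Tinetti gait and balance assessment", then timed up and go, a 6 m walk, single-leg stand and Romberg.
- Section 5 says: "A similar approach will be used to estimate the Receiver Operating Characteristic (ROC) curve for these variables as screening tools for shunt surgery". The similar approach refers back to one-variable-at-a-time logistic regression of patients against healthy controls.
- Section 7.2.1 expects first estimates of the area under the ROC curve (AUC) for "use of gait variables to screen for shunt surgery".

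On what is collected, the study summary calls the design a "Cross-sectional, controlled study" and gives follow-up as not applicable. The outcomes in 4.2 contain no shunt item. Section 9.1 lists the routine-care data that enter the analysis: history, examination, brain MRI, CSF results, clinical gait and balance tests around the lumbar puncture, neuropsychology and HADS. It has no shunt item either. Section 5 mentions later management only as part of routine care.

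On how patients are classified, section 6 places the neurophysiotherapist's gait and balance testing around the tap test "prior to reaching a consensus diagnosis in the multidisciplinary team meeting (NPH MDT". Section 3 says that the change in mobility after lumbar puncture is how likely shunt response is judged.

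**The concern.** A ROC curve needs two values per patient: the test result and a reference status. The protocol supplies the first and leaves the second undefined. A statistical analysis plan can choose the ROC method, but it cannot analyse a shunt outcome that the protocol does not list for collection, and it cannot make a circular reference independent.

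The direction of the error matters. Section 2 hopes that 3D analysis will raise the sensitivity of the tap test so that fewer treatable patients are missed, and section 4.1 says that the tap test has a low negative predictive value. The patients of interest are therefore those whom the clinical tests call negative and 3D analysis calls positive. A reference derived from the clinical tests tends to label these patients negative, so 3D analysis is marked down where it would be most useful. Recruiting more patients would not remove this bias.

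**Working it through.** **1. Stated figure.** There is none to reproduce. Section 7.2.1 declines a power calculation and gives no target AUC.

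**2. Candidate references.** Each one that the text allows is set against what the protocol says about it.

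| Possible reference | What the protocol says | Consequence |
|---|---|---|
| MDT or shunt decision | Clinical gait tests before and after the tap test feed the MDT (6). Other inputs are neurology, neuropsychology, MRI and CSF markers | Comparators sit partly inside the reference |
| Clinical tap-test responder or not | Section 1 plans responder thresholds in relation to standard clinical assessment | Even more circular: the comparators are the rating |
| Patients v healthy controls | The literal sense of a similar approach in section 5 | Measures diagnosis. Section 4.2 already lists this as a separate task |
| Response after shunting | Not listed in 4.2 or 9.1 | Would address the question, but is not planned |

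**3. Size of the circularity (illustration; every input is assumed).** True response rate 60%. The clinical score C, the 3D score G and the other evidence O are normal with unit SD and independent given true response. Each is shifted in responders by d = √2 × z(AUC):

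- AUC 0.75: d = 1.414 × 0.674 = 0.95
- AUC 0.85: d = 1.414 × 1.036 = 1.47

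C and O have a true AUC of 0.75. The reference calls positive the top 60% of w × C + (1 − w) × O, where w is the weight of the clinical tests. Apparent AUCs from 400,000 simulated patients:

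| w | C | G, if truly 0.75 | G, if truly 0.85 |
|---|---|---|---|
| 0 | 0.59 | 0.59 | 0.63 |
| 0.25 | 0.72 | 0.61 | 0.66 |
| 0.50 | 0.87 | 0.62 | 0.67 |
| 0.75 | 0.97 | 0.61 | 0.66 |
| 1.00 | 1.00 | 0.59 | 0.63 |

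With w = 0 the true order is kept. With w = 0.25 a true 3D advantage of 0.85 − 0.75 = 0.10 becomes an apparent deficit of 0.72 − 0.66 = 0.06. With w = 0.50 the deficit is 0.87 − 0.67 = 0.20. With w = 1 the clinical AUC is 1.00 by construction, whatever the truth.

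**4. What an independent outcome would give.** Hanley-McNeil variance, with a = A/(2 − A) and b = 2A²/(1 + A):

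SE² = [A(1 − A) + (n₁ − 1)(a − A²) + (n₀ − 1)(b − A²)] / (n₁n₀)

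For A = 0.80 and an assumed 12/8 split of the 20 patients, a = 0.667 and b = 0.711:

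SE² = [0.160 + 11 × 0.0267 + 7 × 0.0711] / 96 = 0.951/96 = 0.0099, so SE = 0.100 and the 95% interval is 0.60 to 1.00.

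At 18/2 the SE is 0.138 and the interval 0.53 to 1.00. An independent outcome would remove the circularity but would still give only a rough pilot estimate.

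**The case against.** The strongest defence is that this is a pilot. Section 7.2.1 promises only initial estimates and treats significance as indicative. That excuses wide intervals, so the calculation in step 4 is not a criticism of the plan. It does not excuse a missing or circular reference, which is a matter of bias.

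Four stronger readings are tempting, and the documents do not support them.

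- **Shunt data cannot exist because observation stops early.** The last column of the patient schedule is "after day 7 post tap test", but that table covers research procedures only. It also omits the clinical gait tests, which are plainly analysed. Shunt decisions would arise in routine care. The better evidence is that 4.2 and 9.1 do not list them.
- **The MDT decision is the planned, or the only possible, reference.** The protocol never names it. Section 6 speaks of a diagnosis and not of a shunt decision, and the MDT draws on other evidence. The circularity is therefore conditional and partial.
- **3D results reach patients or clinicians before the shunt decision.** Section 5 surveys participants' "reaction to the results using a questionnaire", but nothing says when results are released or that the MDT sees them.
- **Hypothesis (iii) cannot be tested.** It concerns sensitivity at demonstrating change. Before-after scores bear on that without any shunt outcome.

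The simulation also has limits. The weights are unknown, and 3D and clinical scores were taken as independent given true response. Both measure gait, so a shared component would raise the apparent 3D AUC and narrow the gap.

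**Conclusion.** The point holds for the shunt-screening analysis and for nothing else. Sections 4.2, 5 and 7.2.1 promise shunt-screening performance and a ranking of 3D against clinical tests, while no reference is named and no shunt decision, surgery or response is listed as data. An MDT or shunt decision, or a clinical tap-test rating, would contain the comparators and favour them. Patients versus controls would answer a different question.

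The direction of the bias follows from the text, on the condition that one of the clinically derived references is used. Its size does not follow from the text. Under the assumed inputs the ranking reverses even at a clinical weight of 0.25, but the figures are illustrative. Patient-control discrimination and the before-after change comparison stand as planned.

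**What to change.** Amend sections 4.2, 5 and 7.2.1 as follows, and add the new items to the routine-care data listed in 9.1.

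1. Add shunt decision, shunt status and routine post-shunt outcome to the data collected, extracted from the existing clinical record. Report gait variables against post-shunt outcome descriptively.
2. If the MDT decision is used as the reference, say so, label the result as agreement with current practice, and do not rank clinical against 3D ROC curves on it.
3. Otherwise, drop the shunt-screening claim and limit ROC analysis to discrimination between patients and controls.

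The cost is protocol wording and a few extra record fields, with no new visits or tests. The headline claim becomes weaker. Post-shunt outcome will exist only for patients who are shunted, so it says nothing about those not offered surgery. That is why the report should stay descriptive.

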# 6 STUDY SETTING

People with iNPH will be recruited from the regional specialist NPH clinic at The Manchester Centre for Clinical Neurosciences (MCCN) at Salford Royal Hospital, Northern Care Alliance, UK where they are assessed as part of their clinical routine by a senior neurologist with specialist interest in cognitive neurodegenerative disease, by a senior neuropsychologist with specialist interest in differential diagnostic assessments of patients with dementing disorders, advanced MRI scanning of the brain, lumbar puncture for cerebrospinal fluid neurodegeneration markers and clinical examination of gait and balance before and after TT carried out by a neurophysiotherapist prior to reaching a consensus diagnosis in the multidisciplinary team meeting (NPH MDT).

Healthy controls will be recruited in two ways. They may be spouses/carers of people with iNPH or they may be people from the general public who have responded to the study advertisement. We will aim to recruit the same number of controls as patients with a similar age and sex distribution but will not undertake individual matching.

Both groups will undergo the same laboratory-based testing protocols to assess their gait and balance in the gait laboratory at the MMU. Participants in the control group will be invited to attend a single testing visit at the gait laboratory. Participants with iNPH will be invited for a second test session the day after tap test to assess the effects of the procedure on gait (change score on outcome measures). Should the patient not feel well then this visit may have to be cancelled.

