# ROLES AND RESPONSIBILITIES OF STUDY MANAGEMENT COMMITEES/GROUPS & INDIVIDUALS

We have consulted a group of patients and carers living with iNPH for their views on the purpose of the study, and its accessibility, in terms of the potential burden of participating and the ease of understanding the participant information sheets. Their feedback was invaluable, and they expressed keen interest and gratitude for such a study given the significant impact the condition has on their quality of life.

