# 2 RATIONALE

Currently, the comparison of suspected prevalence in epidemiological studies and the recorded number of treatments per year suggests that the condition is largely under-recognized in the world (9). This under-recognizion of iNPH leads to continued suffering in many of those who are never diagnosed. We believe that the proposed project is both innovative and pioneering: in this first proof-of-concept study we aim to use advanced 3D gait analysis, which has not been used before in this context, to identify and quantify gait parameters typical for iNPH. Such methods could prove more sensitive at capturing changes when evaluating effects of CSF drainage procedures and at monitoring the efficacy of the permanent treatment, the surgical placement of a small plastic tube (shunt) draining fluid out of the fluid filled space in the brain (ventricle) into the abdomen (peritoneum), a VP shunt, than routine clinical assessments. It may also help to identify which individual or combination of clinical markers are most useful in the absence of 3D gait analysis. If they increased the sensitivity of the Tap Test to select candidates for shunt surgery, this would help avoid missing potential patients who should be offered treatment. Furthermore they could pick up early any deterioration in shunted patients or help document an improving trajectory after shunting.

In consultation with people with iNPH and their carers, both within the service and as part of a formal Patient & Public Involvement exercise, they have reported a significant toll of the condition on their quality of life. They were grateful that the condition was being studied and hoped to support any research which would improve understanding of iNPH. Studying a condition which affects the elderly is particularly important as many in this patient group feel forgotten about. In some cases, they feel as if their ailments are attributed to age-related changes, and hence are of less importance to healthcare providers. In conducting this research, we hope to improve awareness and understanding of the condition, and also the quality of lives of people with iNPH and their carers

\*Sponsor's representative: [name], Managing Director of Research & Innovation Northern Care Alliance NHS Foundation Trust, [name] email: [contact]

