## 4.1 Objectives

Our primary objective is to identify key gait and balance variables that can objectively characterise the mobility impairment in iNPH and that will also serve as measures to accurately quantify changes in mobility and balance before and after lumbar puncture to remove cerebrospinal fluid (CSF tap test or TT), a standard clinical procedure to assess whether patients may benefit from permanent treatment with a shunt. Whilst the emphasis will be placed on objective laboratory-based measures, this work will also seek to validate robust clinical measures to support clinic-based assessments as potential surrogate measures and for instances where sophisticated gait analysis may not be accessible. We hypothesise that

- those with iNPH will exhibit decreased gait velocity (slower walking), increased step width variability, unsteadiness (increased centre of mass trajectories), reduced joint ranges of motion, and poorer balance test scores, when compared to age-matched controls;
- (ii) gait outcome variables will improve following tap test; and
- (iii) in view of the low negative predictive value but high specificity of the TT gait analysis will be more sensitive than clinical assessments at demonstrating change.

Secondary characterization objectives will aim to quantify general levels of everyday activity with a fitbit, psychological factors such as mood and levels of anxiety, quality of life and carer burden (the latter in patients only), and expectations and experience of gait analysis in healthy control participants and people with iNPH. We hypothesize that general levels of mobility (i.e. in everyday activity) will increase following TT; psychological factors (e.g. mood, expectations) may be considered as potential confounding, mediating and response variables.

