# 7.2.2 Sampling technique

All people with suspected iNPH referred to the MCCN at the NCA are assessed in the regional specialist iNPH clinic. The study will exclusively recruit people with iNPH from this clinic. Participation will be offered to all eligible people with iNPH.

Healthy volunteers can be relatives/friends/carers of people with iNPH but participation will also be offered by advert to members of the general public.

We will recruit until we have 20 controls and 20 patients before and after TT and retain those with partial data.

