## 7.3 Recruitment

#### 7.3.1 Sample identification

People with iNPH will all be recruited by the consultants/nurse of the regional specialist NPH clinic at The Manchester Centre for Clinical Neurosciences at Salford Royal Hospital, Northern Care Alliance, UK. They may either be localised from the waiting list for lumbar puncture or directly when seen in clinic.

Study participation will be offered to healthy volunteers who may be spouses/carers/friends of people with iNPH, to university staff, to people registered on join dementia research, to people studying at the university of the third age (U3A), via "shine", a UK charity dedicated to people with iNPH, social media (Twitter and any others) and other local retirement groups by advert.

Transport costs for 40 participants at £ 35 are available if required. A £25 inconvenience payment will be given to each participant.

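### Spouses and carers of people with iNPH can be healthy controls without limit and are not identified, so control values for the secondary measures, most clearly EQ-5D-5L, may be shifted by the disease

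*Protocol*

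**What the plan says.** Three sections of the protocol describe where controls come from. Section 6 (Study setting): "They may be spouses/carers of people with iNPH or they may be people from the general public who have responded to the study advertisement". Section 7.2.2 (Sampling technique): "Healthy volunteers can be relatives/friends/carers of people with iNPH", with the general public reached by advert. Section 7.3.1 (Sample identification): "Study participation will be offered to healthy volunteers who may be spouses/carers/friends of people with iNPH", followed by other channels such as university staff, a research register, a charity for the condition, social media and retirement groups. None of them limits the proportion of carers.

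The same document reports that the condition weighs on those consulted. Section 2 says of people with iNPH and their carers that "they have reported a significant toll of the condition on their quality of life", and ends with the hope of improving "the quality of lives of people with iNPH and their carers". The section on study management groups, describing a consultation with patients and carers, has "given the significant impact the condition has on their quality of life".

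The secondary objectives in section 4.1 cover activity by Fitbit and "psychological factors such as mood and levels of anxiety, quality of life and carer burden (the latter in patients only"), and they refer to both controls and patients. Under section 5, controls complete HADS and EQ-5D-5L when they attend the gait laboratory and wear a Fitbit for 7 days either side of the gait assessment. The same section says that "carer burden will be assessed with the Burden Scale for Family Caregivers (patients only, part of the clinical routine").

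The eligibility filters in sections 7.1.1 and 7.1.2 deal with health conditions, injury, surgery, medication and ability to take part. The healthy-volunteer schedule in Appendix 2 lists demographics and medical history. Neither mentions carer or spouse status.

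**The concern.** A control group shows what a measure looks like without the disease. For gait and balance, a healthy spouse of similar age serves that purpose well. For quality of life, and perhaps for mood and daily activity, a person who lives with or looks after someone with iNPH may not be unexposed. If carers score worse than other people of their age, the control mean moves towards the patients and the descriptive contrast between the groups shrinks. This would be a systematic shift that a larger sample would not remove, and adjustment for age and sex would not address it.

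There is also a possible double role. The protocol does not require that a carer control be linked to an enrolled patient, but it does not prevent it. In that case one person could be the subject of the Burden Scale on the patient side and a healthy reference on the control side.

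The remedy depends on data collection. If carer status is not captured when controls are screened, no analysis plan can separate the two kinds of control later. Section 9.1 also promises an open-access dataset, whose users would have the same difficulty.

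**Working it through.** The protocol gives no figure to reproduce. Section 7.2.1 sets 20 patients and 20 unmatched controls and states that a power calculation would not be appropriate. The calculation below is therefore illustrative.

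**Inputs**
- n = 20 per group (section 7.2.1).
- p, the share of controls who are spouses or carers: not given. Assumed 0.25 to 0.5. The protocol permits anything from 0 to 1.
- s, the shift in a carer's score towards the patients, in SD units: not given. Assumed 0.2 to 0.5.

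**Bias in the patient-control difference** = p × s

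| p | s = 0.2 SD | s = 0.5 SD |
|---|---|---|
| 0 | 0 | 0 |
| 0.25 | 0.25 × 0.2 = 0.05 | 0.25 × 0.5 = 0.125 |
| 0.5 | 0.5 × 0.2 = 0.10 | 0.5 × 0.5 = 0.25 |
| 1 (every control a carer) | 0.20 | 0.50 |

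**Sampling error of a standardised difference**
- Standard error = √(1/20 + 1/20) = √(2/20) = 0.316 SD.
- Approximate 95% half-width = 1.96 × 0.316 = 0.62 SD.

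**Bias relative to the standard error**, for p from 0.25 to 0.5
- Smallest: 0.05 / 0.316 = 0.16.
- Largest: 0.25 / 0.316 = 0.79.

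**Precision lost by leaving carers out**
- p = 0.25 leaves 15 controls: √(1/20 + 1/15) = 0.342 SD.
- p = 0.5 leaves 10 controls: √(1/20 + 1/10) = 0.387 SD.

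**How far the text supports a shift in each measure**
- EQ-5D-5L: direct. The consultation statements concern quality of life, although they pool patients and carers.
- HADS: inference. Carer burden is measured, but the protocol does not say that carers' mood is altered.
- Fitbit activity: inference, and even the direction is not established.
- Gait and balance (primary, section 4.2): no mechanism is shown.

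**The case against.** The strongest reply is that the protocol plans no formal patient-control test of these measures. The between-group regression in section 5 concerns gait and balance variables, and the one directional secondary hypothesis in section 4.1 is a rise in activity after the tap test, which is a contrast within patients. Significance values are to be read as indicative only. This stands and limits the importance of the point. It does not remove it, because section 4.1 still sets out to quantify these measures in both groups, and readers will compare them.

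A reader might infer that control mood, quality of life and activity are in fact altered by iNPH. The documents do not support that. The carer share could be zero, only quality of life has direct support, and the size of any shift is unknown.

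A reader might also infer that the primary result is biased, since section 4.1 names mood as a possible confounder or mediator. That remark directly follows the tap-test activity hypothesis, and section 5 considers the gait variables one at a time, so no path from control mood to the primary comparison is shown.

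It may further seem that carers should be barred from the reference group for these measures. That is a debatable trade: volunteers from the university and retirement groups may be unusually healthy, which would bias the contrast the other way.

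Finally, it can be said that a carer-status item is CRF or SAP detail. The choice of subset can indeed be left to an SAP. The source of controls and the screening schedule are protocol matters, however, and the schedule shown lists no such item.

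**Conclusion.** The point holds as a minor improvement to the design. Spouses and carers may be controls without limit and are not identified in the control schedule, while the protocol reports an effect of the condition on the quality of life of the patients and carers consulted. The control reference for EQ-5D-5L may therefore be shifted by the disease, and by inference so may those for HADS and Fitbit activity.

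Under the assumed 25% to 50% share and 0.2 to 0.5 SD shift, the bias is 0.05 to 0.25 SD, or about 0.2 to 0.8 of a standard error. At the lower end it is negligible; at the upper end it is worth knowing about but still below the sampling error. It is zero if no carers enrol or if caring does not change the scores. The size rests entirely on those two assumptions. The finding concerns secondary, descriptive measures only.

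**What to change.** Keep spouses and carers eligible. In the healthy-volunteer schedule in Appendix 2, add a screening item recording whether the control is a spouse or carer of a person with iNPH and, if so, whether that person is an enrolled patient. The second part identifies anyone who also stands behind a patient's Burden Scale score. Ask it of every control, whatever the recruitment channel, since the charity route in section 7.3.1 could also bring in carers.

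State in section 5 that control EQ-5D-5L, HADS and Fitbit results will be reported for all controls and again with spouses and carers excluded. The gait and balance analyses need no change.

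The cost is one CRF field, a sentence of protocol text, and less precision in the subset: the standard error rises from 0.32 to about 0.34 SD if a quarter of controls are carers and about 0.39 SD if half are.
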